2. HYPOTHESIS AND OBJECTIVES

1. Hypothesis

Specific Aim 1. In a randomized sham-control trial (n=60), determine the efficacy of home TTNS in SCI.

Hypothesis 1.1: Those in the TTNS group will be able to reduce their OAB medication dosages while maintaining continence compared to controls over a period of 3 months.

Hypothesis 1.2: Symptoms of NGB measured by the Neurogenic Bladder Symptom Score (NBSS) and a voiding diary (VD) will be reduced in the TTNS group compared to controls.

Specific Aim 2. Determine the impact on quality of life using TTNS at home.

Hypothesis 2.1: Incontinence-related QOL (I-QOL) will be increased in the TTNS group compared to the controls and from baseline.

Hypothesis 2.2: Anticholinergic side effects will be decreased in the TTNS group at 3-months compared to the controls and from baseline.

2. Primary Objectives

OBJECTIVE: to advance the science and care around bladder function and management among people with spinal cord injury/disease (SCI/D) and NLUTD with TTNS (and if so, we anticipate translating this research to other populations with NLUTD). Specifically, we seek to demonstrate that TTNS will improve NLUTD in SCI/D by:

1. intervening acutely with neuromodulation of the neurogenic bladder via TTNS to maintain bladder capacity by reducing pathologic reflexes, DH and DSD;
2. altering pathologic autonomic nervous system (ANS) responses and reducing autonomic dysreflexia (AD).
3. improving the quality of life (QOL) of those living with SCI/D by providing a feasible, non-pharmacologic, and dignified intervention for NLUTD that can be performed at home;

In this proposed study, we seek to provide evidence for overall objective #3 using home TTNS. We hypothesize that TTNS can be used in the home setting to maintain continence while reducing OAB medication dosages and improve quality of life.

Primary Objective 1: Evidence of TTNS efficacy with reduced OAB medication dosage

Primary Objective 2: Evidence of TTNS efficacy with reduced NGB symptoms as measured by the NBSS and the Voiding Diary

3. Secondary Objectives

Secondary Objective 1: I-QOL scores will be increased in the TTNS group compared to the controls

Secondary Objective 2: Anticholinergic side effects will be reduced in the TTNS group compared to the controls.

4. Potential Risks and Benefits:

a. End Points - Efficacy

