Primary Objective 1: Evidence of TTNS efficacy with a greater proportion of bladder medication reduction in the TTNS group compared to the control group. Time to achieve this endpoint will be approximately 3 months after subject recruitment, anticipated 1 year to complete all subject recruitment.

Primary Objective 2: Evidence of TTNS efficacy with reduced NGB symptoms as measured by the NBSS and the Voiding Diary. Time to achieve this endpoint will be approximately 3 months after subject recruitment, anticipated 1 year to complete all subject recruitment.

b. End Points- Quality of Life

Secondary Objective 1: Improved QOL in the TTNS group compared to the controls at the end of the 3-month trial, based on I-QOL scores. Time to achieve this endpoint will be approximately 3 months after subject recruitment, anticipated 1 year to complete all subject recruitment.

Secondary Objective 2: Decreased anticholinergic side effects in the TTNS group compared to the controls at the end of the 3-month trial, based on an anticholinergic side effect survey. Time to achieve this endpoint will be approximately 3 months after subject recruitment, anticipated 1 year to complete all subject recruitment.

c. End Points - Safety

Urinary Tract Infection (UTI) risk:

We expect the rates of morbidity to be the same between those who participate and those who do not. However, because UTI is directly related to the bladder, we will focus on the occurrence of UTI. Based on literature, the overall rate of UTI in SCI is about 2.5 episodes per patient per year. As a result, we expect to see 0.6 episodes per patient during the 3-month study period. Based on that, we construct the stopping rules to stop at 20% UTI rate using lower 90% exact Blyth-Still-Casella confidence bounds. If the number of patients with UTI exceed 3 in the first 5 patients, 4 in the first 10 patients, or 5 in the 14 patients, then patient accrual will be paused pending a review by a medical advisory board comprised of SCI experts.

Bladder medication discontinuation risk:

- Worsened incontinence

Electric Stimulation Risks:

Electric stimulation is commonly performed on the extremities of those with spinal cord injury at the study institution. There are few adverse reactions to electric stimulation. The common ones include:

- Pain with electric stimulation: in these cases, the intensity is reduced until it is comfortable.

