6. METHODS AND ASSESSMENTS

- a. Physical exam will be performed per usual care at TIRR, by the attending SCI physicians. Data will be retrieved from the electronic medical record and placed into the data spreadsheet. Missing data will be requested from the attending physician or directly from the patient.
- b. Transcutaneous Tibial Nerve Stimulation (TTNS) will be placed by trained research assistants in the clinic to determine if the subject meets I/E criteria. Skin inspection will be performed before and after the trial stimulation session at the electrode sites. Blood pressure will also be monitored during this trial for an additional safety measure to ensure autonomic dysreflexia is not occurring.
- c. The Bladder diary will be used to collect data use of TTNS with amperage and presence of toe flexion, pain score 0-10, as well as incontinence episodes and volumes. The research assistant (RA) will call weekly to capture the written data and monitor progress with the protocol.
- d. The RA will also perform the survey outcome measures (NBSS, I-QOL, CD-RISC, GSE, Medication adherence surveys and anticholinergic side effect questionnaire) at baseline every 4 weeks, 6 weeks and at 3-months. Surveys can be conducted over the telephone.

2. Randomization and Blinding

Subjects will be randomized to either TTNS or sham control (1:1) using a block size of 4 and stratified based on complete/incomplete SCI to ensure the equal allocation of the most severely injured in the two groups. The PI will be blinded to randomization and treatment allocation, managed by the research assistant.

3. Contraception and Pregnancy Testing

Females of childbearing age will have to adhere to medically recommended contraception if sexually active with men, such as condoms and/or birth control pills.

4. Study Visits and Procedures

- *Screening Visits and Procedures*

Screening will be performed in the SCI clinic by the PI or co-I SCI attendings.

Those that meet the I/E criteria will be approached for the study by the PI or co-I attendings. They have until the study period is complete to decide whether they want to participate. However, they will have to return to clinic to have the TTNS trial performed and the directions for home use.

- *Study Visits and Procedures*

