11. SAMPLE SIZE AND STATISTICAL METHODS

1. Determination of Sample Size

Sample size will be determined from **Aim 1.1**. Assuming that 40% of the subjects in the control group are able to reduce their bladder medications (placebo effect), the study would require a sample size of 21 for each group (i.e. a total sample size of 42), to achieve a power of 80% for detecting a difference in proportions of 43% between the two groups (83% in TTNS group –40% in control group) at a two sided p-value of 0.05. Accounting for 40% dropout, we will recruit 30 subjects in each arm for a total of 60 subjects. In **Aim 1.2**, the NBSS has demonstrated responsiveness to change after bladder chemodenervation with a mean difference of 11.8 (11),²² which would require a sample size of 20. For **Aim 2.1**, a 7±17 point improvement in the I-QOL score was observed after 4 weeks of TTNS use in our pilot study. We expect the control group to have minimal improvement in I-QOL scores due to placebo effect, estimated as 3 points. With power of 80% and a more conservative standard deviation of 4 points, we need a sample size of 22 in total by two-sample two-sided t-test at a type I error rate of 0.05. The sample size determined by Aim 1.1 is sufficient for this aim.

2. Statistical and Analytical Plans

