Patients will be randomized to control and TTNS at a 1:1 ratio by computer-generated sequences, with stratified allocation in blocks of 4 controlling for complete SCI, with the investigator blinded to the treatment allocation. Changes in outcomes listed in Aim 1 and 2 will be compared between groups by two-sample two-sided t-test or Wilcoxon rank-sum test. Descriptive statistics and mean plots will be provided for the longitudinal measurements. Multilevel mixed-effects regression models will be used for longitudinal analyses of treatment effects, controlling for confounding variables including age, sex, severity of SCI, compliance (number of sessions), and OAB medication dosages. Multiple testing will be adjusted by Bonferroni correction if necessary. Non-random missing data will be analyzed using the method in Ibrahim and Molenberghs.²³ Considering the unknown long-term effects of TTNS, we may not see significant treatment effect on some outcomes by conventional (frequentist) analyses. We plan a Bayesian analysis (with either skeptical or neutral priors) to estimate the probability (with 95% credible intervals) of treatment effect. Conventional analysis will be performed in SAS 9.4 (SAS Institute, Cary NC) and Bayesian analysis will be performed in R 3.5.0 using packages like R2WinBUGS.

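### Section 11.2 does not say whether Aim 1.1 is tested as a responder proportion, for which the trial is sized, or as a change in dose, and its named tests omit the randomisation stratum

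*Combined protocol and SAP*

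**What the plan says.** The protocol words the primary medication outcome in two ways. Section 2, under Primary Objectives, has "Evidence of TTNS efficacy with reduced OAB medication dosage", which reads as a quantity. Section 2, under End Points - Efficacy, has "Evidence of TTNS efficacy with a greater proportion of bladder medication reduction in the TTNS group compared to the control group", which reads as a share of subjects.

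Section 11.1 follows the second wording. Aim 1.1 sets the sample size, with a control rate of 40%, a TTNS rate of 83%, and 80% power for "detecting a difference in proportions of 43% between the two groups" at a two-sided 0.05 level. That gives 21 per group.

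Section 11.2 gives one between-group method for every outcome of both aims: "Changes in outcomes listed in Aim 1 and 2 will be compared between groups by two-sample two-sided t-test or Wilcoxon rank-sum test". No chi-square, Fisher, Cochran-Mantel-Haenszel (CMH) or logistic analysis appears anywhere in the document. The section also plans longitudinal mixed models with covariates that include severity of SCI, compliance and OAB medication dosages.

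Section 6, under Randomization and Blinding, says that allocation is "stratified based on complete/incomplete SCI", in blocks of 4.

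**The concern.** A t-test or rank-sum test on changes is the usual language for a numerical outcome, while the endpoint and the power calculation concern a yes/no outcome. A statistician following section 11.2 could reasonably compare mean or ranked change in dose. Subjects may take up to two different anticholinergics, and no common dose scale is given. That result would answer a different question from the one the trial was sized for. Leaving both the variable and the test open also allows the choice to be made after the data are seen, on the outcome that set the sample size.

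The second issue is the stratum. Allocation is balanced on completeness of injury because the investigators consider it important, yet the named two-sample tests do not use it. If completeness predicts who can reduce medication, an unstratified test is conservative and loses power.

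**Working it through.** **1. Reproduce the stated sample size.** Inputs from section 11.1: p1 = 0.83, p2 = 0.40, d = 0.43, two-sided alpha 0.05 (z = 1.960), power 80% (z = 0.842). The mean rate is (0.83 + 0.40)/2 = 0.615. With the pooled variance under both hypotheses:

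n = 2 × 0.615 × 0.385 × (1.960 + 0.842)² / 0.43² = 0.4736 × 7.849 / 0.1849 = 20.1, rounded up to 21 per group.

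This matches the plan, so the figure is a two-proportion calculation. The usual power formula at n = 21 gives (0.43 × √21 − 1.960 × √0.4736) / √(0.83 × 0.17 + 0.40 × 0.60) = (1.971 − 1.349)/0.617 = 1.007, a power of 84.3%.

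**2. Named tests on a yes/no responder.** On a 0/1 outcome with N = 42, both tests are functions of the Pearson chi-square:

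- The t-test (40 df, critical value 2.021) rejects when chi-square ≥ 42 × 2.021² / (40 + 2.021²) = 3.89.
- The tie-corrected Wilcoxon rejects when chi-square ≥ 3.841 × 42/41 = 3.94.
- Pearson itself uses 3.84.

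Summing the two binomial distributions exactly at 21 per group:

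| Test | Power, 83% vs 40% | Type I error, both 40% |
|---|---|---|
| t-test | 83.2% | 4.3% |
| Wilcoxon | 83.2% | 4.3% |
| Pearson chi-square | 85.1% | 5.0% |
| Fisher exact | 74.3% | 2.0% |

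On this reading the stated power holds, and the t-test and Wilcoxon are equivalent. Fisher would need 23 per group to reach 80%, but the plan does not name it.

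**3. Named tests on change in dose.** Power needs a mean difference and a standard deviation. Neither is given for dose, so no power can be calculated and the 80% cannot be carried over.

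**4. The stratum.** The documents give no stratum sizes or rates, so what follows is illustration. Assume strata of 11 and 10 subjects per arm. In the strong-strata case the rates are 95% (TTNS) vs 60% (control) in one stratum and 70% vs 18% in the other. These average to the planned rates: (11 × 0.95 + 10 × 0.70)/21 = 0.83 and (11 × 0.60 + 10 × 0.18)/21 = 0.40. The null case has 60% and 20% in the two strata, the same in both arms. By simulation:

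| Case | Unstratified chi-square | CMH |
|---|---|---|
| Power, completeness not prognostic | 85.1% | 83.6% |
| Power, strong strata | 87.0% | 90.6% |
| Type I error, null 60%/20% | 3.1% | 4.9% |

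A t-test on the responder indicator gives 85.1% power and 2.6% type I error in the two strong-strata rows.

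**5. Does the mixed model close the gap?** It adjusts for severity of SCI, so the plan is not silent on severity. But it is longitudinal, is not tied to the responder proportion, and lists OAB dosage as a covariate. Dosage is the Aim 1.1 outcome itself, so the model cannot serve as the Aim 1.1 test as written.

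**The case against.** The strongest reply is that nothing is broken. The endpoint section and the sample size both speak of proportions, so Aim 1.1 can be read as a yes/no outcome, and a t-test or Wilcoxon on a 0/1 variable is close to a chi-square. That is correct as far as it goes. On that reading the named tests exceed 80% power at 21 per group, and still do at 18 per group (80.8%; 30 per arm less the 40% dropout in section 11.1) and at 27 per group (92.2%; 60 less the 6 dropouts in section 5, split evenly).

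A reader might therefore infer too much from the mismatch, in three ways:

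- That the stated 80% power does not belong to the planned test at all. The documents do not support this. It fails to carry over only if change in dose is tested.
- That the unnamed test decides whether 80% is reached. Of the tests in the first table, only Fisher falls short at 21 per group, and the plan never mentions Fisher.
- That the plan ignores severity altogether, or that omitting the stratum risks false positives. The mixed model includes severity, and the omission makes the test conservative.

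What the reply does not settle is which variable is tested. The Primary Objectives wording supports a dose analysis, section 11.2 does not choose, and no responder is defined. CMH is also not the only sound choice; logistic regression with the stratum as a covariate would serve.

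**Conclusion.** The concern holds as a gap in specification. The plan does not fix whether Aim 1.1 is a responder proportion or a dose change, names no test for a proportion, and gives no rule for choosing between the two tests it does name. For a dose-change analysis the 80% power has no basis. For a yes/no responder it is about 83% at 21 per group, so the sample size is not undermined by the choice of test.

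Omitting the stratum is a smaller matter. Under the assumed strong strata it costs about 4 points of power against an unstratified chi-square (90.6% − 87.0% = 3.6) and brings the type I error down to about 3% from about 5%. Those figures depend on stratum rates and near-equal stratum sizes that the documents do not give. The change is worth making because it concerns the outcome that sized the trial and costs almost nothing.

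**What to change.** In section 11.2, state that Aim 1.1 is the proportion of responders at week 12. Define the responder before unblinding: what counts as a reduction, how two medications are combined, and how the continence condition in Hypothesis 1.1 enters. Reconcile the two wordings of the objective in section 2 with that definition.

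Analyse it with one pre-specified test adjusted for complete/incomplete SCI, for example CMH with a Mantel-Haenszel risk difference and 95% confidence interval. Keep the t-test or Wilcoxon for the questionnaire scores.

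In section 11.1, tie the power statement to that test: about 84% at 21 per group for CMH if completeness is not prognostic.

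The cost is wording only, with no extra data. The downside is about 1.5 points of power against an unstratified chi-square (85.1% − 83.6%) if completeness turns out not to matter, which still leaves power above 80% at 21 per group.

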4. TRIAL SCHEDULE

Table 3. Study Timeline

Task	Year 1				Year 2			
	1	2	3	4	1	2	3	4
Obtain IRB approval								
Register study with www.clinicaltrials.gov								
Subject screening and recruitment (n=60, ~2-6/month)								
Baseline assessments								
Neurogenic Bladder Symptom Score (NBSS) (SA 1.2)								
Incontinence quality of life (I-QOL) (SA 2.1)								
Anticholinergic Side Effects (SA 2.2)								
Collection of Voiding Diary Weekly								
Overactive Bladder Medication dosage (SA 1.1)								
Cath frequency, volumes, and incontinence (SA 1.2)								
Compliance								
Evaluate the efficacy of TTNS at home (SA 1)								
Evaluate the impact of TTNS on quality of life (SA 2)								
Analyze SA 1 & SA 2								
Present findings								
Development of manuscript(s)								

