Medication reduction protocol: Subjects will be using up to 2 anticholinergic OAB medications. Subjects generally use similar medications with a common approach- maximize one medication before adding a second medication. The PI will provide a weekly weaning schedule, individualized for each subject. No changes will occur during the first 2 weeks of TTNS. Starting week 3, the secondary OAB medication will be halved if possible, otherwise discontinued. Should the subject tolerate this, weaning will continue until one medication is discontinued, then the other. If the subject does not tolerate weaning, they will remain on the lowest, tolerable dose and we will attempt weaning the following week.

- Information gathered:
 - Clinical demographics, morbidity, and Neurologic Exam findings from interview with subjects, exam, and EMR review.
 - Bladder diary will include:
 - use of TTNS with amperage and presence of toe flexion, and pain score 0-10
 - log of catheterization, volumes
 - log of incontinence episodes
 - Description of other observed changes, including but not limited to: fatigue, vision changes, mental status, bowel program changes, and sexual function changes.
 - I-QOL at baseline initial visit and then at 3-month follow-up. Can be conducted over phone.

- NBSS at baseline and every 4 weeks (monthly) and at the 3-month follow-up. Can be conducted over phone.
- Anticholinergic survey at baseline and then at 3-month follow-up. Can be conducted over phone.
- TTNS satisfaction survey at 3-month follow-up. Can be conducted over the phone.
- Information will be tabulated on an Excel spreadsheet on my personal work desktop, password protected. Any paper data (bladder diary) will be de-identified and retained in a locked drawer in the locked office of the PI.
- General self-efficacy at baseline, week 6 and at the end of the trial. Can be conducted over the phone.
- CD-RISC at baseline, week 6 and at the end of the trial. Can be conducted over the phone.
- The medication and TTNS adherence survey at baseline then every 4 weeks. Can be conducted over the phone.
- The medication and TTNS % survey at baseline then every 4 weeks. Can be conducted over the phone.

1. Summary of Study Design

A randomized control trial of TTNS v sham-control in chronic SCI (n=60) performing intermittent catheterization on OAB medications will be performed to address the following Specific Aims:

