Subjects will have their first study visit after their normal clinic visit. Once consented, we will trial TTNS for a response of toe flexion. If they have a response, they will be included in the study. If no response or not tolerating electric stimulation, they will not be included in the study.

Participants will have direction in clinic on the use of the Stamobil+, including written, oral, and smartphone images/video if they have access.

The electric stimulation protocol will use stimulation frequency of 10 Hz and pulse width of 200ms in continuous mode for 30 minutes daily, beginning as soon as possible. The goal is 5 days per week of TTNS use for 3-months.

Subjects will be called weekly to capture the information of the TTNS log and to monitor progress of protocol. They will also be reminded to change electrodes weekly. 3 days prior to the NBSS call, the RA will contact the subjects to remind them to begin recording in their voiding diary for 2 days.

- *Final Study Visit:*

Upon completion of the 3-month study period, final voiding diary information will be collected and the post-trial questionnaires will be conducted.

- *Post Study Follow up and Procedures*

The data will be statistically analysed in the post-study follow up. Subject participation is not required.

- *Discontinuation Visit and Procedures*

If withdrawal occurs, no evaluation will be required for the final study visit, regardless of the withdrawal reason. There are no safety risks in withdrawing from this study at any point. OAB medications can be resumed at the prior efficacious dose.

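### Incontinence episodes are to be compared as changes unadjusted for baseline: the tests are valid but give up power that a baseline-adjusted analysis would recover at almost no cost

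*Combined protocol and SAP*

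**What the plan says.** Section 11, Statistical and Analytical Plans, sets the between-group comparison in one sentence: for every Aim 1 and Aim 2 outcome, the change is tested between arms with a "two-sample two-sided t-test or Wilcoxon rank-sum test". The voiding diary falls under it, because Primary Objective 2 in Section 2 reads "Evidence of TTNS efficacy with reduced NGB symptoms as measured by the NBSS and the Voiding Diary". The bladder diary in Section 5 includes a "log of incontinence episodes". The timeline in Section 4 (Table 3) lists "Cath frequency, volumes, and incontinence (SA 1.2" as diary content. No single diary endpoint is named, and Section 11 gives no effect size, variance or power for the diary.

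The same paragraph adds a second analysis: "Multilevel mixed-effects regression models will be used for longitudinal analyses of treatment effects". The covariate list for these models is given as "controlling for confounding variables including age, sex, severity of SCI, compliance (number of sessions), and OAB medication dosages". It does not include the baseline value of the outcome. The paragraph gives no distribution or link and does not say which analysis is primary.

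The recording window differs between sections. In Section 6, Study Visits and Procedures, the research assistant contacts participants 3 days before each NBSS call to "remind them to begin recording in their voiding diary for 2 days". Section 3, Withdrawal Criteria, pays for two diary days a month. Table 3 in Section 4 and the schedule of events in Section 5 show diary collection every week.

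**The concern.** On the 2-day reading, the episode count is small and noisy. Subtracting the baseline count assumes that each extra leak at baseline predicts exactly one extra leak at week 12. When the two counts are only moderately correlated, this adds baseline noise to the comparison. The entry criteria in Section 3 set no minimum leakage, so some participants may start at zero and have no room to improve.

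What is at stake is precision on part of a primary objective, and on the continence side of Hypothesis 1.1. An imprecise comparison could leave a real change in leakage undetected, although the baseline count and the stratum needed to sharpen it are already collected.

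**Working it through.** **The plan's own figure.** None exists for the diary. Trial size comes from Aim 1.1 (83% against 40%, 80% power, two-sided 0.05), stated as 21 per group. The unpooled formula gives 7.849 × (0.83×0.17 + 0.40×0.60) / 0.43² = 7.849 × 0.3811 / 0.1849 = 16.18. With continuity correction, (16.18/4) × [1 + √(1 + 4/(16.18×0.43))]² = 20.6, so 21. The figure reproduces, but it says nothing about the diary.

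**Why differencing costs power.** Let the baseline and follow-up counts have common variance σ² and correlation ρ. Per participant, the error variance is:

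- change score: 2σ²(1−ρ)
- ANCOVA: σ²(1−ρ²)
- ratio, ANCOVA to change: (1+ρ)/2

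At ρ = 0.42, the count correlation in the middle simulated case below, the ratio is 0.71. The change score then needs about 1/0.71 = 1.41 times as many participants. A true halving also shrinks follow-up counts in the treated arm, so subtracting the whole baseline overcorrects further.

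**Inputs for the simulations.**

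- From the documents: 1:1 allocation, 30 per arm, two-sided 0.05. Section 5 expects 6 losses, so (60−6)/2 = 27 per arm. Two diary days (Sections 3 and 6).
- Assumed, because the documents do not give them: leakage rate, between-participant spread, baseline to follow-up correlation, treatment rate ratio.

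**Model A.** Poisson counts with correlated log-normal rates, 27 per arm, 0.5, 1 or 2 episodes per day, log-rate variance 0.5-1.0, correlation 0.5-0.7, rate ratio 0.5. Power across the 12 settings:

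- t-test on change: about 16-54%
- ANCOVA on raw counts: about 27-80%
- regression of log(episodes+0.5) on its baseline: about 31-77%

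**Model B.** Gamma-Poisson counts, 30 per arm, rate ratio 0.5. Rows with gamma shape 1.5 and visit-to-visit SD 0.5 on the log scale:

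| Episodes/day | t-test on change | Wilcoxon on change | ANCOVA, raw counts | Negative binomial, calibrated to 5% size |
|---|---|---|---|---|
| 0.5 | 23% | 22% | 38% | 42% |
| 1 | 31% | 34% | 52% | 56% |
| 2 | 39% | 44% | 66% | 71% |

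Over all 12 Model B settings the t-test has 19-79%, Wilcoxon 19-74% and ANCOVA 30-94%. ANCOVA gains 11-27 points over the t-test, and the calibrated negative binomial gains 12-32. Most of the recoverable power therefore comes from baseline adjustment, and little from a count distribution.

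**Type I error.** The t-test and Wilcoxon run at about 4-6%. The uncalibrated negative binomial test runs at 5-8% with 30 per arm and up to 9% with 21 per arm.

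**Sensitivity.** With 21 per arm, the t-test loses 12-21 points against the calibrated negative binomial. At a rate ratio of 0.7 (30 per arm) the loss is 5-9 points, and every method is weak, at 12-31%.

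**Log(episodes+0.5).** In large samples a true ratio of 0.50 comes out at about 0.72-0.74 for 0.5 episodes per day, 0.62-0.66 for 1 and 0.55-0.58 for 2. The constant 0.5 causes the shrinkage.

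**The case against.** The strongest reply is that the change tests are not the whole plan. The same paragraph has mixed-effects models, a method for non-random missing data and a Bayesian analysis. This stands to the extent that the t-test or Wilcoxon cannot be called the only analysis. As written, though, the models do not clearly repair the loss. If baseline enters only as one more time point with free arm means, the contrast in change is close to the change-score comparison; if baseline is a covariate, it is close to ANCOVA. The plan does not say which. The models also condition on session count and OAB dosage. Both arise after randomisation, and dosage reduction is itself the Aim 1.1 outcome.

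A second reply is that a halving of leakage is not the stated target. Hypothesis 1.1 speaks of maintaining continence, and the Aim 1.2 measure that was sized is the NBSS. This also stands, and it limits the weight of the point.

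A reader might infer that small, skewed counts make the planned tests wrong. The calculations do not support that: both tests hold their size, and ANCOVA on the same raw counts recovers most of the loss. A reader might also infer that a halving would usually be missed because of the test chosen. The documents cannot support that either, since t-test power ranges from 16% to 79% across assumed rates, and the adjusted analysis itself starts at 27%. Nor does the diary stipend show that incomplete diaries are expected, because Section 3 presents it as a measure against non-compliance.

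**Conclusion.** The point holds as a loss of efficiency, with no fault in validity. For incontinence episodes, the planned comparison of changes leaves out an adjustment for baseline that is already available.

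If leakage is truly halved, adjustment adds roughly 11-27 percentage points of power under Model B, and Model A moves the range from about 16-54% to about 27-80%. At a rate ratio of 0.7 the gain is about 5-9 points. The direction was the same in every setting run, but the size rests wholly on assumed leakage rates, spread, correlation and effect. It also rests on a 2-day window, which the documents do not settle, and on episodes being the diary measure of interest, which they do not state. Adjustment does not help participants who start at zero.

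This is a worthwhile low-cost change to the SAP.

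**What to change.** 1. For incontinence episodes, replace the test on change with a pre-specified ANCOVA: week-12 episodes per diary day on arm, baseline episodes per diary day and the complete/incomplete SCI stratum. Leave out post-randomisation covariates (sessions completed, OAB dosage). Report the adjusted difference with a 95% CI, and state how the mixed-effects models rank against it.
2. If a ratio is wanted, take it from a quasi-Poisson or negative binomial model with log diary days as offset and log baseline count as covariate. State how zero baseline counts enter the log. Obtain the p-value by permuting arm within stratum, because the plain negative binomial test is liberal at this size.
3. Do not report the exponentiated coefficient from log(episodes+0.5) as a ratio of episodes, since it turns a true 0.50 into about 0.55-0.74.
4. Reconcile the 2-day diary texts (Sections 3 and 6) with the weekly ones (Sections 4 and 5), so that the same window is used at baseline and week 12.

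The cost is SAP wording and slightly more analysis work. No extra participants or data are needed.
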